5.2.1 Change from Baseline

Definition	Reporting Details
Change from Baseline	= Post-Dose Visit Value – Baseline
% Change from Baseline	= 100 x [(Post-Dose Visit Value – Baseline) / Baseline]

NOTES:

• The baseline will be displayed along with Visit name on all summary displays.

5.3 Examination of Covariates, Other Strata and Subgroups

5.3.1 Covariates and Other Strata

Baseline will be included as a covariate in the efficacy analyses, wherever applicable.

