- 10. Inject the contents into a 250cc bag of normal saline for injection

11. Properly label the infusion bag with the subject ID, D.O.B, preparation date, time and expiration and cover it with an amber bag.

Investigational Product Assignment (Randomization and Blinding)

A total of 24 eligible subjects will be randomized to either placebo (12) or active drug (12) (HB-adMSCs) in a 1:1 balanced design. The randomization will be applicable only to eligible subjects, if a subject is not eligible during the screening process for study participation, this subject shall not me randomized to any group.

Randomization will be conducted using the REDCap randomization module. REDCap does not use an algorithm to dynamically randomize subjects, but rather a pre-determined, stratified and permutated randomization schedule. The module allows for creating a custom allocation list, which serves as a lookup table for deciding how to randomize subjects. The allocation table is stratified to achieve even study treatment distribution within the following subgroups. Raw coded values corresponding to the table are in parenthesis following their representative category.

- Parkinson's severity (Mild vs Moderate):
 - Mild severity (1) (MDS-UPDRS score < 13 AND Carbidopa/levodopa < 375mg/day) (if taking)
 - Moderate severity (2) (MDS-UPDRS > 13 OR Carbidopa/levodopa ≥ 375 mg/day) (if taking)
- Age: ≤ 50 (1) vs > 50 (2)
- Sex: Male (1) vs Female (2)

Controlling Blinded Information

REDCap system's user privileges can be used to allow only certain users to be able to set up the randomization, perform the randomization, or view the allocation information. All REDCap end users will be blinded and will not have access to the randomization information with exception to the unblinded pharmacist and the personnel who will be responsible in setting up the randomization schedule and performing the randomization.

Blinding for Dose Administration

All subjects, investigators, and site staff will be blinded to treatment assigned.

For the preparation of the investigational product, Unblinded pharmacist (UP) will inject the investigational product into a 250 ml sodium chloride (Saline) infusion bag, cover it with an amber plastic bag and apply the label before delivering it to study site.

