7.1.4.1. Statistical Methodology Specification

Primary endpoint will be analyzed using the Mann-Whitney U Test (or Wilcoxon Rank-Sum Test) for the comparison of HB-adMSCs 200MM vs. Placebo.

Sensitivity analysis

Sensitivity analysis will be performed on Efficacy analysis set using a repeated measurements ANOVA model to evaluate the robustness of using parametric method. If the normality of dataset shows significant violation from the presumption of normality, the parametric method will not be performed.

All primary endpoint efficacy measurements available at post-baseline at scheduled measurements will be analyzed using Repeated Measures ANOVA. The model will include treatment, visits as fixed factors. The within subject factor is visit and with 7 levels (Weeks 4, 8, 16, 24, 32, 42 and 52). The between-subjects factor is treatment (HB-adMSCs 200MM or Placebo).

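### Allocation is stratified by severity, age and sex, but no efficacy analysis uses these factors; if they are prognostic, the primary test is conservative and loses power

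*SAP*

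**What the plan says.** The protocol section on investigational product assignment describes "a pre-determined, stratified and permutated randomization schedule" and gives its purpose: "The allocation table is stratified to achieve even study treatment distribution within the following subgroups". There are three two-level factors: severity (mild or moderate, from an MDS-UPDRS score and the carbidopa/levodopa dose), age (up to 50, or over 50) and sex. Allocation is 12 per arm. The block size is not given.

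SAP 5.3.1 is headed as covering covariates and other strata, but its only content is "Baseline will be included as a covariate in the efficacy analyses, wherever applicable". SAP 7.1.4.1 states: "Primary endpoint will be analyzed using the Mann-Whitney U Test (or Wilcoxon Rank-Sum Test) for the comparison of HB-adMSCs 200MM vs. Placebo". SAP 7.2.4.1 does the same for the secondary endpoints, and SAP 5.6 repeats the rule for both. For the sensitivity repeated-measures ANOVA, SAP 7.1.4.1 states: "The model will include treatment, visits as fixed factors". The protocol's mixed model (Statistical Methods) lists no strata either. Neither document gives a reason for leaving them out.

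**The concern.** Stratified allocation balances the arms on the stratification factors. If those factors predict the outcome, the difference between arms varies less from one randomisation to the next than it would under simple randomisation. An unstratified rank test does not know this, because its null variance still contains the variation between strata. The test then rejects less often than its nominal 5% under the null, and less often than it could when the treatment works.

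Baseline adjustment as planned does not settle the matter. A Mann-Whitney test cannot take a covariate, and the listed terms of the repeated-measures model do not include baseline. The severity code also carries levodopa dose, which baseline Part II does not. With 12 per arm and no power calculation in either document, there is little power to spare.

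**Working it through.** **Inputs from the documents.** N = 24, 12 per arm (protocol). Three binary factors give 2 x 2 x 2 = 8 cells, so on average 24/8 = 3 patients per cell. The primary test is at 5%, two-sided (SAP 2.3). SAP 5.4 also places Part II at Week 52 in a Holm procedure with eight endpoints that starts at 2.5/8 = 0.3125%.

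**Inputs assumed.** The documents give no effect size, SD, power or prognostic strength, so there is no planned figure to reproduce. The effect is taken as 1.2 SD. For scale, 12 per arm has 80% power (normal approximation) at (1.960 + 0.842) x sqrt(2/12) = 1.14 SD. R2, the share of variance in Week 52 change explained by severity, is varied. Outcomes are normal with no dropout.

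**Check by hand.** With perfect balance within strata, the arm difference has variance proportional to 1 - R2, while the unstratified test uses a variance proportional to 1. Its true size is then roughly 2 x Phi(-1.96 / sqrt(1 - R2)):

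- R2 = 0.10: 1.96/0.949 = 2.07, size 3.9%.
- R2 = 0.20: 1.96/0.894 = 2.19, size 2.8%.
- R2 = 0.30: 1.96/0.837 = 2.34, size 1.9%.

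**Simulation at the 5% level.** Permuted blocks of 2 or 4 in the eight cells, severity mostly split 50/50 or 25/75, 2,500 to 6,000 trials per scenario. At 2,500 trials the Monte Carlo error is about 0.4 points for size and 0.8 for power. Ranges span the separate runs.

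| R2 (severity) | Mann-Whitney size | Mann-Whitney power | van Elteren by severity, power |
|---|---|---|---|
| 0 | 4.4-5.6% | 75-78% | 74-76% |
| 0.05 | not tabulated | 77-79% | 76-78% |
| 0.10 | 3.6-4.5% | 76-79% | 78-80% |
| 0.20 | about 3% (3.1-3.8%) | 76-80% | 82-85% |
| 0.30 | 2.2-3.0% | 78-80% | 88-89% |

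Simulated sizes sit slightly above the hand formula, as expected when small cells cannot be perfectly balanced. At R2 = 0.20 the stratified test has size 4.8-5.2%.

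**Which adjustment is feasible with 24 patients.** A van Elteren test over all eight cells has power 61-68% at R2 = 0 and 66-73% at 0.10, below the planned test. A linear model with the three factors as main effects has 76-78% at R2 = 0, 81-82% at 0.10 and 87-90% at 0.25.

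**If the prognostic effect is spread over all three factors.** At a total R2 of 0.25 split equally, severity-only van Elteren gains little (about 79% against 77-78%), while the three-factor linear model has 87-88%.

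**At the first Holm step (0.3125%, 1,500 runs).** With R2 of 0.10 or less, exact Mann-Whitney power is 33-37%. Van Elteren with the usual normal approximation has 26-31%, and a permutation version 31-36%. At R2 = 0.20 the permutation version has 42-43% against 32-35% for Mann-Whitney. The reference distribution therefore matters.

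**The case against.** The strongest objection is that the loss is conditional. A reader might infer that the primary p-value is too large and that power is certainly being lost. The documents do not support that. Nothing in them says how well severity, age or sex predict change in Part II, and the endpoint is a change score, which may already remove part of the severity effect. At R2 = 0 the planned test has its nominal size and the stratified test is slightly worse. Nor is this a validity error: the planned test controls type I error, and conservatism is an average property, not a statement about any one realised p-value. All of this stands.

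Three further objections also stand and shape the fix. The benefit at modest R2 is small. A van Elteren test with a normal approximation would cost power at the Holm thresholds. And the severity code is not fully defined: mild requires a score below 13 and levodopa below 375 mg/day, while moderate requires a score above 13 or levodopa of 375 mg/day or more. A score of exactly 13 with levodopa below 375 mg/day fits neither, and which MDS-UPDRS score is meant is not stated.

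In addition, patients excluded under the efficacy-set and missing-data rules can disturb the balance within strata. The simulations had no dropout and do not measure this.

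None of these explains why factors important enough to stratify on are absent from every efficacy analysis.

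**Conclusion.** The omission is certain; its consequence is conditional. If the strata are prognostic for Week 52 change in Part II, the planned Mann-Whitney test is valid but conservative and less powerful than it need be. Using the table above, the stratified test breaks even at an R2 of about 0.05. It gains about 1-3 points at 0.10, about 4-6 at 0.20 and about 8-10 at 0.30, and loses about 1.5-3 at 0. These figures rest on an assumed 1.2 SD effect, normal outcomes, no dropout, the 5% level, and severity as the factor that carries the prognostic information. This is a matter of efficiency, worth changing because the change is cheap and the potential gain exceeds the potential loss.

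**What to change.** Before unblinding:

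- In SAP 7.1.4.1 and 7.2.4.1 (and the matching sentence in 5.6), replace the unstratified test with a Wilcoxon (van Elteren) test stratified by the severity code as randomised in REDCap. Specify an exact or permutation reference distribution that re-randomises within strata, because the normal approximation loses power at the small Holm thresholds in SAP 5.4.
- In SAP 5.3.1, name severity, age group and sex as main-effect factors in the parametric model. Do not cross all eight cells in any analysis.
- Reconcile the severity definition in the protocol: state which MDS-UPDRS score it uses and how a score of exactly 13 was coded.
- If the strata are to be left out after all, give the reason in SAP 5.3.1.

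The cost is SAP wording and a few lines of code, since the codes already exist in the allocation table, plus about 1.5-3 points of power if severity turns out to be unrelated to the outcome.

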5.3.2 Examination of subgroups

No subgroup analysis is planned.

5.4 Multiple Comparisons and Multiplicity

The multiplicity adjustment will be performed for key efficacy endpoints for the conclusion. The Bonferroni-Holm method is used for the multiplicity adjustment for the hypothesis tests performed for the efficacy endpoints. The multiplicity adjusted for the hypothesis tests for below endpoints,

- Change from Baseline in Total MDS-UPDRS Part I at Week 52
- Change from Baseline in Total MDS-UPDRS Part II at Week 52
- Change from Baseline in Total MDS-UPDRS Part III at Week 52
- Change from Baseline in Total MDS-UPDRS Part IV at Week 52
- Change from Baseline in Total Neuro-Quality of Life Assessments scores (Neuro-QOL) at Week 52
- Change from Baseline in Total Parkinson's disease fatigue scale (PFS-16) at Week
 52
- Change from Baseline in Total Parkinson's disease Questionnaire (PDQ-39) at Week 52
- Change from baseline in Total VAS score at Week 52

Using the Bonferroni-Holm method the p-values will be ordered in increasing order and starts with testing the hypothesis with the lowest p-value on the 2.5/k% level (two-sided), where k is the number of hypotheses in the procedure. If significant, the testing proceeds to comparing the next lowest p-value with 2.5/(k-1)%. The testing will stop at the first non-significant result.

Due to high number of performed tests, the additional statistical corrections will be included in order to correct the p-value and avoid false positive results. As the observed phenomena are biological in nature, p-values will be also examined in such manner that the focus will be on the biological meaning. Both methods are providing more rigorous p-values and help avoiding the false positive interpretations.

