2.3. Statistical Hypotheses

The null hypothesis states that there is no significant difference in primary efficacy endpoint, Change from Baseline in the total MDS-UPDRS Part II score, compared to the value at Week 52, between the HB-adMSCs and Placebo treatment groups. The alternative hypothesis is that there is a significant difference between the HB-adMSCs and Placebo treatment groups, meaning that the treatment was effective. The hypothesis will be tested using 5% significance level (two-sided).

All other secondary endpoints are tested as exploratory analysis. The criteria will be the same as for the primary endpoint, 5% significance level, two-sided tests, which is a standard in biology and medicine.

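### SAP 2.3 and 5.4 give two different success rules for the primary endpoint, and nothing in the supplied text says which governs

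*SAP*

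**What the plan says.** SAP 2.3 defines a single primary efficacy hypothesis, on the change from baseline to Week 52 in the MDS-UPDRS Part II total, and sets its level: "The hypothesis will be tested using 5% significance level (two-sided". Of the rest it says: "All other secondary endpoints are tested as exploratory analysis", and then: "The criteria will be the same as for the primary endpoint, 5% significance level, two-sided tests".

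SAP 5.4 says: "The multiplicity adjustment will be performed for key efficacy endpoints for the conclusion". It lists eight Week 52 endpoints, the second being "Change from Baseline in Total MDS-UPDRS Part II at Week 52". The p-values are ordered from smallest to largest, and the procedure "starts with testing the hypothesis with the lowest p-value on the 2.5/k% level (two-sided), where k is the number of hypotheses in the procedure". It moves on to 2.5/(k-1)% and so on, stopping at the first non-significant result. The primary endpoint has no special place in the order.

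The last paragraph of 5.4 adds that "additional statistical corrections will be included in order to correct the p-value and avoid false positive results" and that "p-values will be also examined in such manner that the focus will be on the biological meaning". It names no method for the former and no decision rule for the latter.

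**The concern.** Both sections decide the same thing, whether the trial may claim an effect on Part II at Week 52, and they use different criteria. Under 2.3 the Part II p-value is compared with 5% and nothing else matters. Under 5.4 it faces a stricter level that can depend on seven endpoints which 2.3 calls exploratory.

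One data set could therefore support either verdict on the primary endpoint. Nothing in the documents suggests an intention to pick the rule afterwards, but nothing supplied fixes it beforehand. The timing is sensitive because SAP 5.5 plans an unblinded interim analysis of primary and secondary efficacy data, with results going to members of the sponsor.

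**Working it through.** **1. Do other sections settle it?**

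- SAP 5.6 sets p = 0.05 two-sided as a default that other sections may displace. That lets 5.4 override the default, but 2.3 states 5% for this specific hypothesis.
- SAP 7.1.4.1 names the Mann-Whitney test for the primary endpoint and gives no level.
- The protocol's Statistical Methods section mentions correction only for post-hoc comparisons, with no method or level.
- The SAP objectives table and 7.2.1 also list Part II at all timepoints as a secondary endpoint. At Week 52 that is the same hypothesis and the same test as the primary.

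The part of the SAP before the objectives table was not available, so this check covers the supplied text only.

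**2. The level.** The plan's figure for the primary is 5% two-sided. With k = 8, the starting levels in 5.4 sum to 8 × 0.3125% = 2.5%, so 5.4 as printed does not reproduce 5%, even for the family. The steps are α/k for k = 8, 7, …, 1:

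- As printed (2.5/k%): 0.3125, 0.357, 0.417, 0.5, 0.625, 0.833, 1.25, 2.5%.
- If 2.5% was meant per tail (5/k% two-sided): 0.625, 0.714, 0.833, 1.0, 1.25, 1.667, 2.5, 5.0%. The family level is then 8 × 0.625% = 5%, but 5% applies to Part II only if the other seven have already been rejected.

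**3. Verdicts by Part II p-value.**

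| Part II p | SAP 2.3 | 5.4 as printed | 5.4 per tail |
|---|---|---|---|
| ≤ 0.003125 | pass | pass | pass |
| > 0.003125 to 0.00625 | pass | depends on other seven | pass |
| > 0.00625 to 0.025 | pass | depends on other seven | depends on other seven |
| > 0.025 to 0.05 | pass | always fails | depends on other seven |
| > 0.05 | fail | fail | fail |

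This takes the Holm steps alone. No Holm level exceeds 5%, so any disagreement has 2.3 passing and 5.4 failing. The unnamed corrections and the biological-meaning step cannot be placed in the table.

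**4. In terms of the test statistic.** The protocol randomizes 12 per arm. With no ties, the exact two-sided p is 2 × P(U ≤ u) under the null distribution of U:

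- U = 22: 0.0029; U = 23: 0.0036; U = 33: 0.0242.
- U = 34, 35, 36, 37: 0.0284, 0.0332, 0.0387, 0.0449.
- U = 38: 0.0519.

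Under 2.3, U ≤ 37 succeeds. Under 5.4 as printed, only U ≤ 22 succeeds whatever the other endpoints show, and U = 34 to 37 always fails.

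**5. How often the rules disagree (illustration).** The documents give no effect size, SD or correlation, so these inputs are assumptions: 12 per arm, eight normal endpoints, correlation 0.3 or 0.6, the other seven with zero, half or equal effect, exact p-values, 100,000 simulated trials per case. Ranges are the minimum to maximum over cases, in %.

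| Part II effect | Passes 2.3 | Passes Holm as printed | Passes Holm per tail | Disagree, as printed | Disagree, per tail |
|---|---|---|---|---|---|
| none | 4.4-4.6 | 0.3 | 0.6 | 4.1-4.3 | 3.8-4.0 |
| 0.5 SD | 19.3-19.6 | 2.9-3.4 | 4.7-5.9 | 16.0-16.6 | 13.5-14.8 |
| 1.0 SD | 60.5-60.9 | 20.7-25.8 | 28.0-36.1 | 34.7-40.0 | 24.3-32.6 |

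In no case did Holm reject Part II when 2.3 did not.

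**The case against.** The best defence is a harmonising reading. On this view 2.3 gives the nominal level, and 5.4, as the dedicated multiplicity section that names Part II at Week 52 and says it serves the conclusion, decides. The only defect left would be the printed 2.5/k%. This is arguable but not conclusive: no sentence gives 5.4 precedence, and 2.3 calls the other seven endpoints exploratory, which does not fit a formal family that can decide the primary.

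The last paragraph of 5.4 can also be read more mildly. Its closing sentence counts two methods, which may be Holm and the biological review, with no third correction. The word *additional* points the other way, so the text is ambiguous and still needs clearing up.

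Three cautions on the numbers stand:

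- The band that always fails exists only on the printed level. On the per-tail reading p = 0.03 can pass, at the last step.
- The U values assume 12 per arm, no ties and an exact test. The efficacy set requires all six infusions and missing data are excluded, so n may be smaller; at 10 per arm the band is U = 21 to 23. Part II is a sum of graded items, so ties are likely. The SAP does not say exact or asymptotic; with a continuity-corrected normal approximation, U = 33 at 12 per arm gives 0.0262 instead of 0.0242 and moves into the band.
- The disagreement rates rest on assumed effects. They illustrate size and are not the ground for requiring a change.

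It is also true that Holm is conservative. That protects the conclusion only if Holm is binding, which is the open question.

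**Conclusion.** The concern holds, and the SAP must be corrected. The success criterion for the primary efficacy endpoint is not uniquely defined: 2.3 and 5.4 differ whether 5.4 is read as printed or per tail. This rests on the text and needs no assumption about effects.

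Confidence in the conflict is high. The statement that nothing resolves it is limited to the supplied text. Under the assumptions above, power for Part II at 1.0 SD is about 61% under 2.3, against 21-26% under Holm as printed and 28-36% per tail, so the choice of rule matters in a trial of 24.

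**What to change.** State one rule for the primary endpoint. Either option is coherent, and the choice is the sponsor's.

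- **Option A**, which fits the single hypothesis in 2.3: remove Part II at Week 52 from the 5.4 list and test it alone, first, at two-sided 5%. Then either report the other seven as exploratory, or test them by Holm at 5/k% (first step 5/7 = 0.714%) only if Part II is significant. The second form also requires amending the 2.3 sentences that make the secondaries exploratory at 5%. State that the Week 52 Part II result listed among the secondary endpoints is the primary test and is not tested again.
- **Option B**: keep the eight-endpoint family, amend 2.3 to say that it decides the conclusion, and state the family-wise level in 5.4 (steps of 5/k% if that level is two-sided 5%).

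Under either option, correct the printed 2.5/k% two-sided level, delete or name the additional corrections, and state that biological meaning does not alter the significance decision.

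Date the change before anyone involved sees unblinded efficacy data, including the interim in 5.5; the supplied documents do not say whether it has taken place. If such data have been seen, report Part II under both the 5% test and the Holm steps as printed, disclose that the SAP conflicted, and do not claim success on a result that meets only the more lenient rule. In that situation Holm becomes the binding rule in effect.

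The cost is SAP text only, with no change to data collection or sample size. Option A with gatekeeping permits secondary claims only if the primary succeeds. Option B lowers power for the primary.

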5.5 Interim analysis

Interim analysis of primary and secondary efficacy data will be performed. Details of the planned displays for interim are provided in **Error! Reference source not found.** Interim analysis will be conducted when at least 10 subjects from each group have completed Week 24.

For the interim analysis, subject-level data will be unblinded. The unblinded analysis of the interim outputs will be done by unblinded independent statistics and programming team, who have access to interim analysis data. An unblinded statistician, not otherwise associated with the project, will perform the interim analysis, which will include the displays shown in the **Error! Reference source not found.**, with delivery priory labelled as "INTER".

These results will be limited to the members of SPONSOR engaged in the discussion of interim analysis results, and will not be shared with the investigators.

